9.2. Sample Size Determination

For Cohort 1, the sample size was based on the need to have an adequately sized safety database of participants on PF-06882961 in an obese population up to 26 weeks of dosing following Phase 2 clinical development. Approximately 420 participants (approximately 60 in each of the placebo and 5 PF-06882961 arms with 1-week titration steps and

approximately 20 in each of the 3 PF-06882961 arms with 2-week titration steps) were to be randomized in the original cohort (Cohort 1). The sample size of Cohort 1 also provided acceptable operating characteristics for decision making based on the primary endpoint, the percent CFB at End of Treatment in body weight.

For Cohort 1, assuming a 25% drop-out rate there would be expected to be approximately 315 completed participants, with approximately 45 completed participants per arm for each of the placebo and 1-week titration PF-06882961 arms. For End of Treatment defined as Week 26, this yields 80% power to detect a placebo-adjusted reduction in body weight of (comparing PF-06882961 to placebo), using a 1-sided t-test at a 5% level and assuming a conservative SD on the loge-scale of for body weight change at Week 26, based on historical internal studies.

For Cohort 2, approximately 49 additional participants were to be randomized to the placebo and 2-week titration PF-06882961 arms (approximately 7 in the placebo and approximately 14 in each of the 3 2-week titration arms). This sample size was selected to provide additional tolerability data on the 2-week titration arms and provide improved operating characteristics of the primary endpoint.

Assuming a 25% drop-out rate, with the combination of placebo and the 2-week titration arms from both Cohorts 1 and 2 (approximately 67 participants randomized to placebo and approximately 34 participants in each of the 2-week titration arms in total) there would be expected to be approximately 50 completed placebo participants and approximately 25 completed participants in each of the 2-week titration arms. For End of Treatment defined as Week 26, this yields 80% power to detect a placebo-adjusted reduction in body weight of (comparing a 2-week titration arm of PF-06882961 to placebo), using a 1-sided t-test at a 5% level, and assuming a conservative SD on the loge-scale of for body weight change at Week 26, based on historical internal studies.

For Cohort 3, approximately 112 additional participants will be randomized (approximately 16 in the placebo and approximately 32 in each of the 3 PF-06882961 arms with 4-week titration steps). This sample size was selected to provide additional tolerability data using 4-week titration steps and provide acceptable operating characteristics for the primary endpoint. Assuming a discontinuation rate of 25%, it is expected that approximately 84 of these participants will complete the study, with approximately 12 completing the placebo arm and approximately 24 completing each of the PF-06882961 arms. For End of Treatment defined as Week 32, this yields 80% power to detect a placebo-adjusted reduction in body weight of (comparing PF-06882961 to placebo) at Week 32, using a 1-sided t-test at a 5% level and assuming a conservative SD on the loge-scale of for body weight change at Week 32, based on historical internal studies. If judged necessary by the sponsor to meet study objectives (for example, if the rate of discontinuation or rate of non-compliance is higher than anticipated), then up to approximately 140 participants may be randomized into Cohort 3, to ensure a sufficient number of completing participants.

Participants who withdraw from the study will not be replaced. Evaluable participants are defined as in Section 9.3.

9.3. Analysis Sets

For purposes of analysis, the following analysis sets are defined for the combined Cohorts 1 and 2, and separately for Cohort 3:

| Participant Analysis Set | Description |
|---|---|
| Enrolled | "Enrolled" means a participant's agreement to participate in a clinical study following completion of the informed consent process. Potential participants who are screened for the purpose of determining eligibility for the study, but do not participate in the study, are not considered enrolled, unless otherwise specified by the protocol. |
| Randomly assigned to study intervention | All participants randomly assigned to study intervention regardless of whether or not study intervention was administered. |
| Evaluable | All participants randomly assigned to study intervention and who take at least 1 dose of study intervention. Participants will be analyzed according to the randomized study intervention. |
| Safety | All participants randomly assigned to study intervention and who take at least 1 dose of study intervention. Participants will be analyzed according to the study intervention they actually received. |

| Defined Analysis Set | Description | |
|---|--|--|
| Estimand Set 1 (related to estimands 1, 2, 3, 4, 5 and 6) | All participants randomly assigned to study intervention and who take at least 1 dose of study intervention. For participants who discontinue study intervention, all subsequent values will be censored. | |
| Estimand Set 2 (related to estimand 7) | All participants randomly assigned to study intervention and who take at least 1 dose of study intervention and do not have major protocol deviations. Major protocol deviations will be reviewed prior to database lock to identify such participants, with further details included in the SAP. For participants who discontinue study intervention, all subsequent values will be censored. | |

| PK Concentration Set | All participants randomly assigned to study intervention and who take at least 1 dose of PF-06882961 and in whom at least 1 concentration value is reported. |
|----------------------|--|
|----------------------|--|

9.4. Statistical Analyses

The SAP will be developed and finalized before any analyses are performed and will describe the analyses and procedures for accounting for missing, unused, and spurious data. This section is a summary of the planned statistical analyses of the primary and secondary endpoints.

9.4.1. General Considerations

Cohorts 1 and 2 will generally be analyzed separately from Cohort 3, with all treatment arms of PF-06882961 and placebo analyzed separately. For Cohorts 1 and 2, reporting of the placebo and the 2-week titration PF-06882961 arms will be based on the combined set of participants from both cohorts, ie, the original cohort (Cohort 1) and Cohort 2.

For Cohorts 1 and 2, End of Treatment is defined as Week 26. For Cohort 3, End of Treatment is defined as Week 32.

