There will be total of approximately 581 participants across all 3 cohorts of this study. In Cohort 1, approximately 420 participants (approximately 60 in each of the placebo and 5 1-week titration PF-06882961 arms and approximately 20 in each of the 3 2-week titration PF-06882961 arms) were randomized. All dosing arms, including placebo, were enrolled simultaneously in Cohort 1. Subsequently, in Cohort 2, approximately 49 additional participants were randomized to the placebo and 2-week titration arms (approximately 7 in the placebo and approximately 14 in each of the 3 2-week titration arms.). Combining Cohorts 1 and 2, there were a total of approximately 469 participants randomized (approximately 67 in the placebo, approximately 60 in each of the 5 1-week titration arms and approximately 34 in each of the 3 2-week titration arms). In Cohort 3, approximately 112 participants will be randomized to 4 additional study arms (approximately 16 in the placebo and approximately 32 in each of 3 PF-06882961 arms with 4-week titration steps).

Randomization is stratified according to biological gender (female versus male), as both tolerability and efficacy may be different between men and women. This stratification is intended to balance the numbers of participants of either gender across treatment arms. In addition, no more than approximately 70% of the trial population will consist of 1 gender, in order to permit adequate representation of both men and women in the trial population.

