6.3.1. Adverse Events

Adverse events (Tier 1, 2 and 3 AEs as described in Section 3.2.2.1) will be summarized by treatment group and overall and in accordance with sponsor reporting standards using the safety analysis set defined in Section 4. The adverse events (AEs) will be sorted in descending frequency within a system organ class.

Incidence and severity of treatment emergent adverse event (TEAE) tables will additionally be produced ('All causality' and 'Treatment related', separately) to summarise the total number of adverse events by preferred term, which will be reported by treatment group and overall.

The following tables and figures related to TEAEs classed as Tier 1 or 2 will be ordered in descending point estimate of risk difference within System Organ Class. If two or more events have the same frequency, they will be sorted alphabetically by preferred term.

TEAEs classed as Tier 1 events will be tabulated by treatment group. Number of participants and percent will be presented, along with the risk difference between each treatment group of danuglipron and placebo. 95% confidence intervals and p-values will also be presented for the comparison. No adjustment for multiplicity will be used.

Tier 1 TEAEs will also be presented graphically. The TEAEs will be presented in a two-panel plot, the left panel will give the proportions of TEAEs observed in a treatment group of danuglipron and separately placebo while the right panel will display the 95% confidence interval for the risk differences for each TEAE. A vertical line corresponding to the value of 0 will be added to the right-hand plot. For the graphical display for tier 1 events, a column containing the p-value for each event will be added to the right-hand side of the forest plot in the right panel. Each panel will be paged by treatment group of danuglipron.

TEAEs classed as Tier 2 events will be summarised and graphically presented similar to Tier 1 events, but no p-values will be presented. No adjustments for multiplicity will also be used.

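### Every planned safety contrast sets one danuglipron arm against placebo; no pooled danuglipron incidence or risk difference is prespecified, and the thresholds for showing an event work against harms spread across arms

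*Protocol*

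**What the plan says.** Protocol 9.2 bases the size of Cohort 1 on "the need to have an adequately sized safety database of participants on PF-06882961 in an obese population up to 26 weeks of dosing". Cohorts 2 and 3 were added mainly for tolerability data and for the operating characteristics of the primary endpoint. For Cohorts 1 and 2 combined, Protocol 4.1 plans a placebo group of about 67 and gives the active arms as "approximately 60 in each of the 5 1-week titration arms and approximately 34 in each of the 3 2-week titration arms". Its numbers for Cohort 3 are "approximately 16 in the placebo and approximately 32 in each of 3 PF-06882961 arms with 4-week titration steps".

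Protocol 9.4.1 has data analysed "with all treatment arms of PF-06882961 and placebo analyzed separately". SAP 6.3.1 states that adverse events "will be summarized by treatment group and overall and in accordance with sponsor reporting standards", and that Tier 1 events are tabulated "along with the risk difference between each treatment group of danuglipron and placebo". Tier 2 events are handled the same way, without p-values. The model contrasts for laboratory, vital-sign and ECG data (SAP 6.3.2.1, 6.3.3, 6.3.4) are also arm against placebo. The treatment labels in SAP 5.2 contain no all-danuglipron group. 'Overall' appears throughout SAP 6.3 and under Discontinuations in SAP 6.6.2, but is not defined.

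SAP 3.2.2.1 makes an event Tier 2 if it reaches 5% in any one standard-titration or placebo group, or 2 participants in any one slow-titration group. Protocol 4.1 equates standard with 1-week and slow with 2-week steps. SAP 6.3.1 also has a frequent-event table, whose entry rule is more than 5% of participants in Cohorts 1 and 2 combined, or in Cohort 3.

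**The concern.** The stated reason for the size of Cohort 1 is the number of people on danuglipron, yet no planned safety output uses that number as a group. Common gastrointestinal events will show up in single arms. The gap concerns less common events. Protocol 2.3.1 lists pancreatitis, renal impairment and acute gallbladder disease as potential class risks, and for events of that kind arm counts of 0, 1 or 2 are hard to read.

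At stake is whether the report gives, as a planned result, the incidence of an event on danuglipron and its difference from placebo with an interval. There is also a selection effect: an event spread thinly over eight active arms may never qualify for a risk difference at all.

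**Working it through.** **Inputs.** Arm sizes are from Protocol 4.1 and the Tier 2 and 5% rules from SAP 3.2.2.1 and 6.3.1. Event rates are assumptions, because the documents give none for safety. All randomized participants are taken as dosed.

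**The plan's own figures.** 67 + 5×60 + 3×34 = 469; 469 + 112 = 581; 420 × 0.75 = 315 completers in Cohort 1. All reproduce. The documents state no precision or detectable rate for safety.

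**Numbers on danuglipron.** Cohort 1: 5×60 + 3×20 = 360. Cohorts 1 and 2: 5×60 + 3×34 = 402. Cohort 3: 3×32 = 96.

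**Precision of one group's incidence.** With zero events, the one-sided 95% upper bound is 1 − 0.05^(1/n).

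| Group | n | Upper bound |
|---|---|---|
| 2-week arm | 34 | 8.4% |
| 1-week arm | 60 | 4.9% |
| All danuglipron, Cohorts 1 and 2 | 402 | 0.74% |
| 4-week arm | 32 | 8.9% |
| All danuglipron, Cohort 3 | 96 | 3.1% |

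**Precision of the risk difference.** The Wald 95% half-width is 1.96 × √(p1q1/n1 + p0q0/n0), with n0 = 67.
- 10% v 5%: n1 = 60 gives 1.96 × √(0.09/60 + 0.0475/67) = 9.2 points; n1 = 402 gives 6.0.
- 3% v 1%: 6.2 points (n1 = 34), 4.9 (n1 = 60), 2.9 (n1 = 402). This is approximate at such low rates.

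**Tier 2.** The 1-week threshold is 0.05 × 60 = 3 participants; the 2-week threshold is 2. The most that can occur without reaching either is 5×2 + 3×1 = 13, and 13/402 = 3.2%. For a true rate p in every active arm, the chance of missing Tier 2 through all of them is P(X ≤ 2 | 60, p)^5 × P(X ≤ 1 | 34, p)^3.
- p = 1% (about 4 events expected): 0.78.
- p = 2% (about 8 events): 0.33.

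Placebo could still trigger Tier 2, but that takes 4 of 67 (0.05 × 67 = 3.35).

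**The 5% table.** If the combined denominator includes placebo, 23/402 on danuglipron (5.7%) with 0/67 on placebo is 23/469 = 4.9%, so the event is left out. It would still surface elsewhere. Twenty-three events exceed the 13 that can escape Tier 2. They also exceed the 5×3 + 3×1 = 18 that can occur with no arm above 5%, so the event would enter the separate table of events above 5% in any arm.

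**'Overall'.** Placebo is 67/469 = 16/112 = 14.3%. Rates of 30% on danuglipron and 10% on placebo would print as (402×0.30 + 67×0.10)/469 = 27%.

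**What pooling does not give.** Power of a two-sided 5% Fisher test against 67 on placebo:

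| True rates | n1 = 34 | n1 = 60 | n1 = 402 |
|---|---|---|---|
| 3% v 1% | 5% | 6% | 0.1% |
| 5% v 1% | 16% | 19% | 11% |
| 8% v 1% | 38% | 45% | 62% |

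Against 0/67, the pooled group needs 24/402 (6.0%) for p ≤ 0.05.

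**Is pooling across cohorts confounded?** The planned placebo share is 60/420 = 7/49 = 16/112 = 1/7, so danuglipron to placebo is 6:1 in every cohort.

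**The case against.** A dose-ranging trial is meant to separate doses and titration speeds, and pooling 40 to 200 mg BID can hide a dose-related harm. SAP 6.3.1 calls the safety analysis exploratory. Tier 1 events get risk differences whatever their frequency, and their list, kept in a Safety Review Plan outside these documents, may include the class risks. An internal committee reviews unblinded safety data at least annually. Sponsor reporting standards, also not in the documents, might define 'overall' or add a pooled column.

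Much of this stands. Arm-level tables should remain the main display, and it is a reading, not a stated definition, that 'overall' includes placebo. That reading is the natural one: SAP 5.2 lists placebo among the treatment groups, and SAP 6.6.1 uses the same phrase for the baseline tables. The exploratory label is a weaker defence, since a pooled summary is a useful way to generate hypotheses about less common harms.

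A reader might infer that uncommon harms cannot be seen. The documents do not support that: counts are tabulated for every arm and can be summed. If 'overall' includes placebo, subtracting the placebo column gives the danuglipron count exactly. A reader might also infer that pooling would supply a test of uncommon harms. It would not, because placebo stays at 67.

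**Conclusion.** The point holds as a gap in prespecification and display. The visible text plans only single-arm contrasts with placebo, and no all-danuglipron incidence or contrast. The loss is in precision: in Cohorts 1 and 2 the zero-event bound is 4.9% or 8.4% by arm against 0.74% pooled, and the half-width at an assumed 10% v 5% is 9.2 against 6.0 points. The arm-by-arm Tier 2 trigger adds to this, since an event of up to 3.2% on danuglipron can go without a risk difference unless it is Tier 1 or common on placebo. The 5% table matters less, because the event in the example would appear in other outputs.

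These figures rest on the planned arm sizes, the assumed event rates and, for the Tier 2 probabilities, one common rate across active arms. The dilution and 5%-table figures also assume that the pooled counts include placebo. The safety-database argument applies to Cohort 1 (360 on danuglipron), not to all 402. It would also be wrong to infer that a pooled contrast must be stratified because the placebo share differs by cohort; by design it is the same in each.

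**What to change.** In SAP 6.3 and in SAP 6.6.2 (Discontinuations):

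- Define 'overall', stating whether it includes placebo.
- Add an all-danuglipron column, excluding placebo, to the adverse event, laboratory flag, vital-sign category, ECG category and IP-discontinuation tables, separately for Cohorts 1 and 2 and for Cohort 3.
- Add a danuglipron-minus-placebo risk difference with 95% CI for adverse events. Stratification by cohort is optional.
- Apply the Tier 2 rule in SAP 3.2.2.1 and the 5% rule in SAP 6.3.1 to the pooled danuglipron group as well as to the present groups.

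The cost is SAP wording plus one column and one contrast from data already collected. The drawback is that the pooled figure averages over doses and titration speeds, so it should be labelled supplementary and read for precision, not as a test. In Cohort 3, with 16 on placebo, the pooled incidence will be more informative than the contrast.

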9.4.1.1. Analyses for Continuous Endpoints

The MMRM model(s) will include treatment, time, strata (females versus males) and treatment-by-time interaction as fixed effects, baseline as a covariate and the baseline-by-time interaction with time fitted as a repeated effect and participant as a random effect. An unstructured correlation matrix will be used, and the Kenward-Roger approximation will be used for estimating degrees of freedom for the model parameters.

Missing values will be imputed as part of the MMRM model assumptions.

9.4.1.2. Analyses for Categorical Endpoints

The logistic regression model(s) will include a term for treatment, strata (females versus males), and baseline will be included as a covariate.

Missing values will be imputed using multiple imputation where the model will include treatment, baseline and strata (females vs. males) and will include all time course data up to Week 26 or Week 32, depending on the cohort. The logistic regression model will be applied to each imputed dataset and the parameter estimates will be combined using standard multiple imputation techniques. Further details will be described in the SAP.

9.4.2. Primary Endpoint(s)

A MMRM analysis (as per Section 9.4.1) of the percent CFB in body weight through End of Treatment will be used to estimate the treatment effect related to the primary Estimand 1. MMRM models will be fitted to the combined Cohorts 1 and 2 data and separately to the Cohort 3 data. Baseline body weight will be included on the log_e-scale. The MMRM models

will be fitted to the CFB of log_e-transformed values to Weeks 2, 4, 6, 8, 10, 12, 16, 18, 22 and 26 for Cohorts 1 and 2 or Weeks 4, 8, 12, 16, 20, 24, 28 and 32 for Cohort 3 from the Estimand Set 1. The modelled mean log_e-differences and 90% CIs for the log_e-differences at the End of Treatment timepoint will be extracted from the model and exponentiated to provide estimates of the relative difference in each PF-06882961 treatment arm reported separately, compared to placebo.

No adjustments will be made for multiplicity.

9.4.3. Secondary Endpoint(s)

For the secondary endpoints described below in the table, models will be fitted to the combined Cohorts 1 and 2 data, and separately to the Cohort 3 data.

| Endpoint | Statistical Analysis Methods |
|--|---|
| Secondary: Response as defined by a body weight loss ≥5% at End of Treatment. | A logistic regression analysis utilizing multiple imputation for missing values (as per Section 9.4.1.2) of participants who achieved a body weight loss ≥5% at the End of Treatment timepoint and those that didn't will be used to estimate the treatment effect related to the secondary estimand 2. Baseline body weight will be included in the logistic regression and multiple imputation analyses. The logistic regression model will be fitted to the End of Treatment timepoint only after multiple imputation has been applied to |
| Secondary: Percent CFB in body weight at Weeks 2, 4, 6, 8, 10, 12, 16, 18 and 22 for Cohorts 1 and 2, and at Weeks 4, 8, 12, 16, 20, 24 and 28 for Cohort 3 | Estimand Set 1. No adjustments will be made for multiplicity. Results related to this endpoint will be obtained from the Primary Analysis model. No adjustments will be made for multiplicity. This analysis will estimate the treatment effect related to Estimand 1. |
| Secondary: Absolute CFB in waist circumference at End of Treatment | Absolute CFB in waist circumference at each planned in-clinic study visit up through the End of Visit Treatment visit will be analyzed using an MMRM model (as per Section 9.4.1.1). Baseline waist circumference will be included as a covariate in the model. No adjustments will be made for multiplicity. Results at the End of Treatment timepoint will be extracted from the model. This analysis will be applied to Estimand Set 1 to estimate the treatment effect related to Estimand 3. |

| Endpoint | Statistical Analysis Methods | |
|---|---|--|
| Secondary: Absolute CFB in waist-to-hip ratio at End of Treatment | Absolute CFB in waist-to-hip ratio at each planned in-clinic study visit up through the End of Visit Treatment visit will be analyzed using an MMRM model (as per Section 9.4.1.1). Baseline waist-to-hip ratio will be included as a covariate in the model. No adjustments will be made for multiplicity. Results at the End of Treatment timepoint will be extracted from the model. This analysis will be applied to Estimand Set 1 to estimate the treatment effect related to Estimand 4. | |
| Secondary: CFB in HbA1c at Weeks 16 and 26 for Cohorts 1 and 2, and Weeks 16, 24 and 32 for Cohort 3 | CFB in HbA1c at Weeks 16 and 26 for Cohorts 1 and 2, and Weeks 16, 24 and 32 for Cohort 3, will be analyzed using an MMRM model (as per Section 9.4.1.1). Baseline HbA1c will be included as a covariate in the selected model. No adjustments will be made for multiplicity. This analysis will be applied to Estimand Set 1 to estimate the treatment effect related to Estimand 5. | |
| Secondary: CFB in FPG at each planned in-clinic study visit up through the End of Treatment | CFB in FPG at each planned in-clinic study visit up through the End of Treatment will be analyzed using an MMRM model (as per Section 9.4.1.1). Baseline FPG will be included as a covariate in the model. No adjustments will be made for multiplicity. This analysis will be applied to Estimand Set 1 to estimate the treatment effect related to Estimand 6. | |

